4. ABSTRACT

Protocol Title: An Observational Post-Authorization Safety Study to Assess the Safety of Ad26.COV2.S Using Health Insurance Databases in the United States 20 October 2022)

Sponsor's Responsible Epidemiologist: PPD PharmD, MSCE, Associate Director Epidemiology (Main Author)

NOTE: The term "sponsor" used throughout this document refers to the entities listed in the Contact Information page(s), which will be provided separately.

SARS-CoV-2 has spread rapidly and globally since its emergence, causing coronavirus disease-2019 (COVID-19). The World Health Organization (WHO) declared that the outbreak constituted a public health emergency of international concern on 30 January 2020 and declared the outbreak to be a pandemic on 11 March 2020.

On 27 February 2021, the United States (US) Food and Drug Administration (FDA), on recommendation by the Vaccines and Related Biological Products Advisory Committee (VRBPAC), granted an Emergency Use Authorization (EUA) for the Ad26.COV2.S vaccine for use in individuals 18 years of age and older based on the totality of scientific evidence available demonstrating that the benefits of the vaccine outweigh the risks. On 20 October 2021, the FDA authorized the use of a single booster dose of Janssen COVID-19 Vaccine as a homologous booster at least 2 months after completion of the primary vaccination, and as a heterologous booster following completion of a primary vaccination with another authorized or approved COVID-19 vaccine. On 19 November 2021, the FDA formally amended the EUA for Janssen COVID-19 Vaccine (Ad26.COV2.S) to authorize the vaccine as a single booster dose following completion of primary vaccination with another authorized or approved COVID-19 vaccine (ie, as a heterologous booster dose) in individuals aged 18 years and older. The dosing interval for the heterologous booster dose is the same as that authorized for a booster dose of the vaccine used for primary vaccination. In addition, the Fact Sheet for Healthcare Providers Administering Vaccine (Vaccination Providers) was updated to state that data support the effectiveness of a booster dose when administered at an interval of longer than 2 months after primary vaccination with the Janssen COVID-19 Vaccine. On 14 December 2021, based on reports to the Vaccine Adverse Events Reporting System (VAERS), a passive surveillance system, the FDA revised the EUA Fact Sheet based on evidence of an increased risk of thrombosis with thrombocytopenia syndrome (TTS) with onset of symptoms approximately 1 to 2 weeks after administration of the Janssen COVID-19 Vaccine. On 05 May 2022, the FDA further revised the EUA, limiting use of the Ad26.COV2.S vaccine "to individuals 18 years of age and older for whom other authorized or approved COVID-19 vaccines are not accessible or clinically appropriate, and to individuals 18 years of age and older who elect to receive the Janssen COVID-19 Vaccine because they would otherwise not receive a COVID-19 vaccine" (US FDA 2022).

Through this protocol, the sponsor plans to conduct a large observational, post-authorization safety study (PASS) aiming to characterize the safety profile of Ad26.COV2.S to inform the scientific community on serious adverse events that could be associated with the use of Ad26.COV2.S.

Research Question and Objectives

This study aims to assess the risk of developing prespecified adverse events of special interest (AESIs) following administration of Ad26.COV2.S.

Objectives

• The primary objective for this study is to assess, in adults aged 18 years and older, the potential association between the occurrence of predefined AESIs and vaccination with Ad26.COV2.S within disease-specific risk periods in individuals exposed to the first dose of Ad26.COV2.S vaccine, as compared with either 1) individuals exposed to at least the first dose of BNT162b2 vaccine for non-acute events or 2) for acute events during a control window within the same individual.

Endpoints

The primary analysis endpoints for this study are to estimate:

- the incidence of anaphylaxis within 0-2 days in individuals vaccinated with the Ad26.COV2.S vaccine
 and in corresponding individuals vaccinated with the BNT162b2 vaccine or during a control window
 within the same individual.
- the incidence of generalized convulsion, arrhythmia, acute kidney failure or acute hepatic failure
 within 1-14 days in individuals vaccinated with the Ad26.COV2.S vaccine and in corresponding
 individuals vaccinated with the BNT162b2 vaccine or during a control window within the same
 individual.
- the incidence of cardiac inflammatory disorders (including myocarditis and pericarditis) or sensorineural hearing loss within 1-21 days in individuals vaccinated with the Ad26.COV2.S vaccine and in corresponding individuals vaccinated with the BNT162b2 vaccine or during a control window within the same individual.
- the incidence of:
 - thromboembolic events: microangiopathy, disseminated intravascular coagulation, deep vein thrombosis, pulmonary embolism, cerebral vein thrombosis, peripheral thrombosis, hemorrhagic or non-hemorrhagic stroke, acute myocardial infarction, coronary artery disease (including acute myocardial infarction), thrombosis with thrombocytopenia within 1-28 days in individuals vaccinated with the Ad26.COV2.S vaccine and in corresponding individuals vaccinated with the BNT162b2 vaccine or during a control window within the same individual
 - heart failure, or stress cardiomyopathy within 1-28 days in individuals vaccinated with the Ad26.COV2.S vaccine and in corresponding individuals vaccinated with the BNT162b2 vaccine or during a control window within the same individual
 - composite endpoints within 1-28 days in individuals vaccinated with the Ad26.COV2.S vaccine
 and in corresponding individuals vaccinated with the BNT162b2 vaccine or during a control
 window within the same individual
 - o venous thrombosis, including pulmonary embolism and deep vein thrombosis
 - o arterial thrombosis, including coronary artery disease and non-hemorrhagic stroke
 - o stroke, including non-hemorrhagic and hemorrhagic strokes
- the incidence of encephalitis (including acute demyelinating encephalomyelopathy and meningoencephalitis), Guillain Barré Syndrome, Bell's palsy, immune thrombocytopenia, thrombocytopenia, and transverse myelitis within 1-42 days in individuals vaccinated with the Ad26.COV2.S vaccine and in corresponding individuals vaccinated with the BNT162b2 vaccine or during a control window within the same individual.
- the incidence of autoimmune thyroiditis, acute aseptic arthritis, multiple sclerosis (including optic neuritis), and Type 1 diabetes mellitus **within 1-365 days** in individuals vaccinated with the Ad26.COV2.S vaccine and in corresponding individuals vaccinated with the BNT162b2 vaccine.

Secondary Objective

• The secondary objective for this study is to describe the number of individuals who received a second dose of Ad26.COV2.S as well as their baseline demographics.

Study Design

This is a retrospective observational study using health insurance claims databases in the US. Eligible individuals will be included in the study from the time of EUA of Ad26.COV2.S in the US, and the study will end at the last date of data availability in each of the databases.

The study design will depend on whether the AESI is an acute or non-acute event. The primary study design for acute events (events expected to occur within 60 days of vaccination) will be a self-controlled risk interval design (SCRI) conducted in the Ad26.COV2.S exposed cohort. For non-acute events, a cohort design will be used to compare individuals exposed to Ad26.COV2.S with concurrent active comparators (individuals exposed to at least 1 dose of BNT162b2 [Pfizer-BioNTech COVID-19 vaccine]). The cohort design with a concurrent active comparator will also be used to assess acute events in sensitivity analyses.

Self-controlled risk interval design (primary study design for acute events)

The SCRI design will compare the risk of the AESIs in a postvaccination risk window to a postvaccination control window within the same individual, in a cohort of individuals vaccinated with Ad26.COV2.S.

Individuals will be followed from the start of the risk window to the end of the control window.

Cohort design with concurrent active comparator (primary study design for non-acute events and sensitivity analysis for acute events)

For the cohort design with a concurrent active comparator, the incidence of AESIs will be compared between 2 vaccine cohorts that will be defined based on their exposure to Ad26.COV2.S or BNT162b2:

- **Exposed cohort**: individuals will have received at least 1 dose of Ad26.COV2.S administered according to US recommendations (Biologic License Application [BLA] approval or EUA). The reference date for the exposed cohort will be the first date of receipt of the vaccine.
- Active comparator cohort: individuals will have been vaccinated with BNT162b2 at any time on or after the start of the study observation period. The reference date of the comparator cohort will be the calendar date of the first dose in the primary series of BNT162b2. Individuals will be matched by propensity scores (PS) and calendar time (within 2 weeks) at the reference date using a 1:4 ratio of exposed to comparator within the Data Partner distributed database, if feasible; the matching ratio will be dependent on the findings of the relative uptake of vaccinations identified during feasibility assessments and monitoring.

COVID-19 vaccines were first administered to priority populations at high risk of severe disease or exposure, including older adults or those with comorbidities. Therefore, information on the presence of comorbidities within 1 year prior to the reference date and older age will be collected and included in the PS models. Additional covariates to be included are listed under Variables.

Cohorts will be defined utilizing existing secondary healthcare data sources. One year of medical and pharmacy insurance enrollment prior to the reference date will be required to determine whether individuals meet the study criteria and to define baseline characteristics. Data on the occurrence of an AESI will be extracted within the 1 year after the reference date.

Follow-up will begin on or the day after the reference date; follow-up time will end at the earliest of the following: date of first diagnosis of AESI, death, disenrollment from the health plan, administrative end of the study (eg, end of available data), end of duration of the risk period specific to the AESI (up to 1 year after the reference date), date of any COVID-19 vaccine that is not the index vaccine, or date of receipt of

an additional or booster dose beyond the authorized primary series (ie, a second dose of COVID-19 in the Ad26.COV2.S cohort or a third dose of COVID-19 vaccine in the BNT162b2 cohort).

Feasibility assessment (monitoring phase)

At study initiation, counts of Ad26.COV2.S vaccine exposures and any mRNA vaccine exposures, including primary vaccination series, baseline characteristics, and the number of AESIs, will be monitored from each database to confirm the feasibility of implementing the planned final analysis in the available data sources for specific AESIs. The crude incidence rate for each AESI in the risk intervals following vaccination for first-dose Ad26.COV2.S vaccinees and first dose of any mRNA vaccinees will be calculated for each individual AESI after excluding individuals with prior evidence of that AESI before cohort entry in specified time windows.

The observation period for the monitoring analysis will start on the launch date of Ad26.COV2.S in the US (27 February 2021).

Setting and Study Population

For the SCRI design, eligibility criteria will be applied separately for analysis of each AESI. Individuals over the age of 18 years at the reference date will be included if they have received a first dose of Ad26.COV2.S vaccine during the study period, experienced the AESI during the risk or control period, and have at least 1 year of continuous medical and prescription drug coverage prior to the date of vaccination until the end of the AESI-specific control interval.

For the active comparator cohort design, individuals over the age of 18 years at the reference date who have at least 1 year of continuous medical and prescription drug coverage for at least 1 year prior to the reference date, and who have not been found to be vaccinated with any COVID-19 vaccine prior to the reference date will be eligible for the overall study cohorts. Each AESI will be analyzed separately. For the analysis of each AESI, individuals with AESI-specific exclusion criteria will be excluded, and analyses will be done in the AESI-specific subcohort.

Variables

Exposure to the Ad26.COV2.S vaccine or BNT162b2 vaccine will be identified using recorded procedure or pharmacy dispensing codes for COVID-19 vaccines (eg, National Drug Code, Current Procedural Terminology, Healthcare Procedure Coding System codes). Where existing linkages with vaccination registries are available within the appropriate Data Partner research databases, the vaccine registry data also will be used to assess exposure.

Population characteristics will be identified based on medical, pharmacy and procedure codes, and insurance enrollment information. The following variables will be used to characterize the study population and will be included in PS models for the cohort design:

- Demographic characteristics (at reference date) such as age, sex, race/ethnicity (if feasible, as determined during the monitoring phase of the study), and a proxy for socioeconomic status (SES), if feasible, calculated using geographic information at least as granular as a patient's 5-digit ZIP code, and geographic location (eg, state or census region)
- Pregnancy status (at reference date)
- Frailty
- 1-year medical history (at reference date)
 - Comorbidities such as cancer, chronic kidney disease, heart conditions, COPD, asthma, sickle cell disease, immunocompromised states, obesity, Down syndrome, and Type 2 diabetes

- Healthcare utilization (eg, mean number of emergency department visits, inpatient visits)
- Medication use (eg, drug class utilization)
- Previous history of COVID-19 (evidence of either of the following):
 - o Diagnosis codes for COVID-19 (yes/no)
 - O SARS-CoV-2 positive laboratory result from NAAT, antigen or serology tests if available (evidence of a positive test, yes/no)

Vaccinations:

- Administration of other COVID-19 vaccine doses from the reference date of the exposed and active comparator cohorts until the end of the follow-up period (to be used to describe primary series completion or receipt of booster doses, and as censoring criteria; not to be included in propensity score models)
- Administration of certain vaccines, such as influenza vaccine, any pneumococcal vaccine, any shingles vaccine, or any human papillomavirus (HPV) vaccine from 1 year prior to the reference date
- Other vaccinations received concurrently with the Ad26.COV2.S vaccine or BNT162b2 vaccine

Evaluation of Safety Outcomes

Within Janssen, a list of AESIs has been created based on current knowledge of the Ad26.COV2.S vaccine and potential risks related to adeno platform vaccine. AESIs will be identified, with a date of diagnosis, using predefined validated algorithms (as possible), based on diagnosis codes (with procedure and/or pharmacy dispensing codes and/or limited to specific medical care settings if applicable to the outcome). Data will be collected on the following AESIs using claims algorithms within disease-specific risk interval periods following the administration of Ad26.COV2.S or BNT162b2:

- Nervous system: encephalitis (including acute demyelinating encephalomyelopathy and meningoencephalitis), Guillain-Barré Syndrome, transverse myelitis, Bell's palsy, Multiple sclerosis, (including optic neuritis), sensorineural hearing loss, generalized convulsion (with and without epilepsy)
- Immune system: autoimmune thyroiditis, immune thrombocytopenia, thrombocytopenia, Type 1 diabetes mellitus, acute aseptic arthritis, anaphylaxis
- Cardiac system: cardiac inflammatory disorders (including myocarditis and pericarditis), microangiopathy, heart failure, stress cardiomyopathy, acute myocardial infarction, coronary artery disease (including acute myocardial infarction), arrhythmia
- Blood and lymphatic system: deep vein thrombosis (DVT), pulmonary embolism (PE), disseminated intravascular coagulation, non-hemorrhagic stroke, hemorrhagic stroke, composite outcome of venous thrombosis (including PE and DVT), composite outcome of arterial thrombosis (including coronary artery disease and non-hemorrhagic stroke), composite outcome of stroke (including non-hemorrhagic and hemorrhagic strokes), cerebral venous thrombosis, peripheral thrombosis, thrombosis with thrombocytopenia
- Renal system: acute kidney failure
- Hepatic system: acute hepatic failure

Case validation to confirm the algorithm and/or disease diagnosis and date of onset may be conducted on AESIs that are judged likely to be misclassified based on clinical expert opinion, prior validation studies (if available), and researchers familiar with the data sources, including the Data Partners. Review of medical records or chronological listing of diagnosis, procedure, and pharmacy dispensing codes in health insurance

claims profiles by clinicians may be conducted, depending on the AESI. For outcomes selected for validation, a strategy for sampling events for validation will consider the rarity of the event.

For the SCRI design, control periods will be the same length as the risk period and the exact timing that control periods will begin will be defined in the statistical analysis plan (SAP). A buffer period may be included between the risk and control periods when the risk period is uncertain. For the cohort design, follow-up will depend on the length of the outcome-specific risk windows.

Data Sources

This study will be conducted using health plan data held by Data Partners that participate in the FDA's Sentinel System, including CVS Health (Aetna), HealthCore (Anthem), Humana, and Optum. These Data Partners update their quality-checked data 3 to 4 times per year; some are updating more frequently with fresher data (ie, shortened data lags) to support FDA-initiated COVID-19 analyses. The study will use the most up-to-date standardized and curated data source available within each Data Partner.

All study data will be accessed with procedures compliant with US subject confidentiality requirements, including the Health Insurance Portability and Accountability Act of 1996 (HIPAA). Where appropriate, as required by local regulations, this study will be undertaken only after the Independent Ethics Committee (IEC)/Institutional Review Board (IRB) has given full approval of the final protocol, any applicable amendments, and the sponsor has received a copy of this approval.

Study Size

Subject to the feasibility assessment, a minimum target sample size of 100,000 individuals in the exposed cohort and 400,000 individuals in the active comparator concurrent cohorts will be included in the comparative cohort study.

Main Statistical Methods

Self-controlled risk interval design (primary study design for acute events)

For the SCRI design in the Ad26.COV2.S exposed cohort, incidence rates of each AESI during the risk period will be compared with the incidence rates in exposed cohort during the control period using a conditional Poisson regression model to estimate incidence rate ratios and 95% confidence intervals (CIs).

Cohort design with concurrent active comparator (primary study design for non-acute events and sensitivity analysis for acute events)

For comparisons of Ad26.COV2.S vaccinees versus BNT162b2 vaccinees, matching on PS and calendar time (within 2 weeks) will be implemented to ensure comparability between the 2 exposure groups on observed covariates. The PS is the predicted probability of an individual being classified in the Ad26.COV2.S exposed cohort versus the comparator BNT162b2 cohort, given a set of observed covariates.

The baseline covariates used to fit the PS model will be those described under Variables.

The propensity to be vaccinated with Ad26.COV2.S will be estimated using logistic regression with vaccination received as the dependent variable and all baseline covariates as independent variables. Individuals receiving BNT162b2 will be matched on PSs to individuals receiving Ad26.COV2.S.

All analyses will be summarized by cohort and by data sources. Demographic and baseline characteristics of the individuals at the reference date will be described in the matched analytic cohort. For continuous/ordinal variables the number of observations, mean, standard deviation, minimum, and maximum will be described. For categorical variables, the number and percent per category will be summarized. Balance of characteristics between the exposure groups will be evaluated with absolute standardized differences.

For the cohort design, incidence rates for each AESI will be calculated by dividing the number of events by the follow-up person-time in propensity score-matched exposure cohorts, and cumulative incidence curves will be estimated by exposure group. Incidence rate ratios and 95% CIs will be estimated with Poisson regression models or another appropriate method to be specified in the SAP. The risk difference will be computed as the difference between the incidence rate in the Ad26.COV2.S-exposed cohort and the incidence rate in the active comparator, BNT162b2 exposed, cohort. Incidence rate ratios will be pooled across data sources using a random-effects model or another appropriate method to be specified in the SAP.

Sensitivity analyses

For events with uncertain risk windows, SCRI analyses with extended risk periods will be considered as sensitivity analyses.

Secondary analyses

To address the secondary objective, the number of individuals in the exposed cohort will be reported by the number of Ad26.COV2.S doses received. Among individuals receiving 2 doses of Ad26.COV2.S, the amount of time between doses and the demographic characteristics for those individuals will be reported.

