Cohorts will be defined utilizing existing secondary healthcare data sources. One year of medical and pharmacy insurance enrollment prior to the reference date will be required to determine whether individuals meet the study criteria and to define baseline characteristics. Data on the occurrence of AESI will be extracted within the 1 year after the reference date.

Figure 2: Cohort Study Design

[figure not shown]
Ad26.COV2.S exposed cohort

Outcome-specific follow-up periods after vaccine receipt

Comparator BNT162b2 exposed cohort

Outcome-specific risk periods after dose 1 for outcomes with risk windows \leq 21 days

Comparator BNT162b2 exposed cohort

If vaccine dose 2 is received during the outcome-specific risk period after dose 1, the risk periods of dose 1 and dose 2 are concatenated into a single risk period, and follow-up ends after the duration of the outcome-specific risk period following dose 2. If vaccine dose 2 is not received, the outcome-specific risk window extends the full length from dose 1.

Outcome-specific risk windows:

- 2 days: anaphylaxis.
- 14 days: generalized convulsion, arrhythmia, acute kidney failure, acute hepatic failure.
- 21 days: cardiac inflammatory disorders, including myocarditis and pericarditis, and sensorineural hearing loss.

- 28 days: microangiopathy, disseminated intravascular coagulation, DVT, pulmonary embolism, hemorrhagic and non-hemorrhagic stroke, acute myocardial infarction, coronary artery disease (including acute myocardial infarction), heart failure, stress cardiomyopathy, venous thrombosis composite endpoint, arterial thrombosis composite endpoint, stroke composite endpoint.
- 42 days: encephalitis (including acute demyelinating encephalomyopathy and meningoencephalitis), Guillain Barré Syndrome, Bell's palsy, immune thrombocytopenia, thrombocytopenia, transverse myelitis.
- 365 days: autoimmune thyroiditis, acute aseptic arthritis, multiple sclerosis (including optic neuritis), Type 1 diabetes mellitus.

Note that follow-up time for the primary analysis will end upon receipt of a booster dose of Ad26.COV2.S or a booster dose of any COVID-19 vaccine.

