8.2.2. Population Selection Criteria

8.2.2.1. Inclusion/Exclusion Criteria for the Self-Controlled Risk Interval Design

For analyses of acute outcomes, individuals will be included in SCRI analyses if the following criteria are met. Note that the eligibility criteria will be applied separately for analysis of each AESI (Additional details regarding requirements for follow-up during the risk and control windows will be defined in the SAP):

- Received a dose of Ad26.COV2.S vaccine during the study period as their first dose of any COVID-19 vaccine
- Experienced the AESI during a risk period (as defined in Table 1) or control period (to be defined in the SAP)

- Did not experience the specific AESI during the pre-event washout period (as defined in Table 1)
- Have at least 1 year of continuous health plan enrollment with medical and prescription drug coverage prior to the reference date and an earliest coverage date on or before 11 December 2020 (to maximize the ability to identify the first COVID-19 vaccine administered during the study period)
- Aged 18 years or older at the reference date

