8.3.5. Follow-Up

8.3.5.1. SCRI Design

Individuals will be followed from the start of the risk window to the end of the control window (Figure 1). Control period definitions will be specific to each AESI and may be the same length or longer than the risk period. Control period definitions, including their placement relative to vaccination and length, will be defined in the SAP, taking into account the rareness and potential seasonality of each AESI. A buffer period may be included between the risk and control periods when the risk period is uncertain as documented in the literature. Postvaccination control windows will be used for the final analyses to avoid healthy vaccinee bias.

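### The abstract makes coverage to the end of the control window a condition of SCRI entry, with no exception for death; Section 8.2.2.1 does not, and applied literally the abstract rule would lower the IRR for AESIs with delayed fatality

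*Protocol*

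**What the plan says.** The abstract, under Setting and Study Population, admits a person to an SCRI analysis if the AESI fell in the risk or control period and if there is at least one year of "continuous medical and prescription drug coverage prior to the date of vaccination until the end of the AESI-specific control interval". Nothing is said about people whose coverage ends because they die.

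Section 8.2.2.1, the detailed list of SCRI criteria, has a different enrolment condition: "Have at least 1 year of continuous health plan enrollment with medical and prescription drug coverage prior to the reference date", together with an earliest coverage date. It sets no coverage condition after vaccination and says instead: "Additional details regarding requirements for follow-up during the risk and control windows will be defined in the SAP".

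Section 8.3.5.1 adds: "Individuals will be followed from the start of the risk window to the end of the control window". It also fixes the side of vaccination on which the control window lies: "Postvaccination control windows will be used for the final analyses to avoid healthy vaccinee bias". The buffer described in Section 8.1.1.1, meant for risk that extends beyond the risk interval, implies that the control window follows the risk window.

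The abstract and the body also differ on control-window length, which affects the size of the effect. The abstract says that "control periods will be the same length as the risk period"; Section 8.3.5.1 says that control periods "may be the same length or longer than the risk period".

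**The concern.** A rule that coverage must last to the end of a later window, with no exception for death, selects cases on survival after the outcome. The selection is unequal. A risk-window case must survive the rest of the risk window, any buffer and the whole control window. A control-window case need survive only the rest of the control window. Fatal cases would therefore be lost more often from the risk window, and the IRR would move toward the null, or below 1 where there is no true effect.

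In a safety study that is the unfavourable direction. SCRI is the primary design for all acute AESIs, including stroke, acute myocardial infarction, pulmonary embolism, disseminated intravascular coagulation and thrombosis with thrombocytopenia. The last of these is listed in Section 6.1 as an identified safety concern.

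**Working it through.** **Inputs from the protocol.** Risk window of 28 days, from the list under Figure 2 ("28 days: microangiopathy, disseminated intravascular coagulation, DVT, pulmonary embolism, hemorrhagic and non-hemorrhagic stroke") and Table 1. Control window after vaccination, taken here as adjacent and of equal length, as the abstract has it. Power from Table 2 in Section 8.5.1: 0.926 for a relative risk of 2 and 100 events.

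**Assumed inputs.** Case fatality f of 5, 10, 20 or 40%, equal in both windows. Time from event to death either even over 30 days or exponential with mean 1 to 30 days. Event days even within each window. Death treated as loss of coverage.

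**Step 1: the plan's own figure.** With the signed-root likelihood-ratio formula, r = 0.5 and β = ln 2:
- A = 2[(2/3)(0.6931) − ln 1.5] = 0.1133
- B = (β²/A)(2/3)(1/3) = 0.943
- power = Φ[(√(100A) − 1.96)/√B] = Φ(1.448) = 0.926

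All 20 cells of Table 2 reproduce to three decimals. The table is not at issue.

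**Step 2: survival required.** Counting whole days, with events on days 1-28 or 29-56 and coverage required to day 56, a risk-window case must survive 28-55 days and a control-window case 0-27 days.

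**Step 3: effect on the IRR.** Observed IRR = true IRR × (share of risk-window cases kept)/(share of control-window cases kept).

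*Deaths even over 30 days, whole days.* The share of fatal cases dead by day 56 is (28/30 + 29/30 + 26)/28 = 0.996 for risk-window events and 13.5/30 = 0.45 for control-window events. At f = 20% the factor is (1 − 0.2×0.996)/(1 − 0.2×0.45) = 0.801/0.910 = 0.880.

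*Deaths exponential with mean τ, continuous time.* The mean share dead for a remaining time between a and b is 1 − [τ/(b−a)](e^(−a/τ) − e^(−b/τ)). At f = 20% and τ = 14 this gives 0.941 for risk-window cases (a = 28, b = 56) and 0.568 for control-window cases (a = 0, b = 28). Kept: 0.812 and 0.886. Factor 0.916.

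| Case fatality | Even over 30 d: factor (IRR 2 reads) | Mean 7 d | Mean 14 d | Mean 1 d |
|---|---|---|---|---|
| 5% | 0.972 (1.94) | 0.987 (1.97) | 0.981 (1.96) | 0.998 (2.00) |
| 10% | 0.943 (1.89) | 0.974 (1.95) | 0.960 (1.92) | 0.996 (1.99) |
| 20% | 0.880 (1.76) | 0.943 (1.89) | 0.916 (1.83) | 0.991 (1.98) |
| 40% | 0.733 (1.47) | 0.862 (1.72) | 0.807 (1.61) | 0.977 (1.95) |

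**Step 4: layout.** At f = 20% and τ = 14, a 14-day buffer takes the factor from 0.916 to 0.907. A 56-day control window takes it to 0.944.

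**Step 5: power.** In the same case, 100 original events at a true IRR of 2 shrink to 100 × (0.812×2/3 + 0.886×1/3) = 83.7, and the IRR reads 1.83. The formula of Step 1 then gives 0.78 instead of 0.926.

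**Step 6: the opposite error.** If the coverage condition were simply dropped and nominal windows used for everyone, people who disenrol early could contribute risk-window events but not later control-window events. Control-window events come 28 days later on average, so the factor is about 1/(1 − m)^(28/30) for monthly disenrolment m: 1.009 at an assumed 1% and 1.029 at an assumed 3%.

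**The case against.** The strongest reply is that the detailed criteria do not contain the rule. Section 8.2.2.1 omits it and defers window follow-up to the SAP, which is not at hand. The Amendment 1 log records that 8.2.2.1 was clarified to match the planned approach and does not list the abstract in that row, so the abstract sentence may simply not have been updated. This stands, and it decides the form of the point. A reader might infer that fatal cases are dropped and that the primary IRR is biased. The protocol does not support that as fact, because nothing in it says that the abstract prevails over the body. Equally, nothing says that the body prevails.

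Second, the link from death to loss of coverage is an inference. The end-of-follow-up lists in the abstract and Section 8.3.5.2 name death and disenrolment separately. Those lists govern the cohort design only, so they neither create nor remove an exemption for the SCRI.

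Third, every fatality input is assumed, and the largest effects need high fatality with deaths spread over weeks. This stands for size, not for direction: with equal fatality in both windows the factor cannot exceed 1. If risk-window cases were more lethal, the bias would be larger.

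Fourth, fatal acute cases remain in the active-comparator cohort analysis of acute events (Section 8.7.5.3), where survival after the event is not an entry condition. That could expose a discrepancy, but it is a sensitivity analysis and does not correct the primary estimate.

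Finally, full coverage serves a purpose: it makes both windows observable. As Step 6 shows, removing the condition altogether would introduce an upward error.

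**Conclusion.** The contradiction between the abstract and Section 8.2.2.1 is certain. The bias is conditional on two things: that the abstract wording governs, and that death is treated as loss of coverage. If both hold, the error runs one way, toward understating risk. At 5-20% assumed fatality and adjacent 28-day windows it is modest, with factors of about 0.99 to 0.88 for deaths spread over days to weeks. It approaches zero for nearly immediate death or low fatality, so AESIs that are rarely fatal are hardly touched. The IRR of 1.47 at 40% fatality with evenly spread deaths is an extreme scenario, not an estimate for any AESI in this study.

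This is a should-fix point, with moderate confidence that the bias would occur in practice.

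**What to change.** Amend the abstract and Section 8.2.2.1 so that they carry the same rule, and carry it into the SAP:

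- Require coverage to the end of the AESI-specific control window, except where coverage ends by death.
- Keep cases who die after the event, using nominal risk and control window lengths. The factor from this mechanism then returns to 1.00.
- Continue to exclude non-death disenrolment before the end of the control window, or model the time actually observed.
- Report the strict full-coverage restriction as a sensitivity analysis.

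State the control-window length consistently in the abstract and Section 8.3.5.1 at the same time.

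The cost is a sentence in each place, a flag in the analysis program and one extra run. No new data are needed, because the cohort design already uses death as an end of follow-up.
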